Research Facility	EUROFINS EVIC PRODUCT TESTING ROMANIA S.R.L. [name]

I have read this protocol and agre protocol and in compliance with all	e to conduct this study in accordance applicable Good Clinical Practices and	with all stipulations of the regulations.
	3)	01 10 0 10

Signature of Principal Investigator Date

Synopsis

Study Number:	ER 19/232		
Current version:	Version 1.0 of 29/11/2019		

Former versions:			
Protocol Title:	Preoperative Skin Preparation Study Following ASTM E1173 Methods to Evaluate the Antimicrobial Capabilities of Four Test Substances		
Planned Sample Size:	This evaluation will be performed with an estimated of a minimum of 50 evaluable sites per product with qualifying treatment day microbial baseline counts.		
	This study is designed to determine the antimicrobial effectiveness of three treatments (A, B and C), intended for use as Patient Preoperative Skin Preparation. The testing methods are based on the standardized test method ASTM E1173-15, Evaluation of Preoperative, Precatheterization, or Preinjection Skin Preparations, and using the requirements specified by in the 2017 FDA 21 CFR Part 310, Safety and Effectiveness of Health Care Antiseptics; Topical Antimicrobial Drug Products for Over-the-Counter Human Use, Final Rule (December 20, 2017). The immediate antimicrobial efficacy will be evaluated in this study.		
Overall Study Design and Plan:	At least 100 subjects will be treated bilaterally with two of the four test materials (A, B, C and Positive Control), one per each side of the groin test site. Subjects will undergo at least a 14-day washout period before Treatment Day. During Treatment Day subjects who meet the Inclusion Criteria will be treated with the study products and samples will be taken before and after treatment application. The cup scrub technique will be used for sampling baseline, 30-seconds and 10-minutes on the Treatment Day.		
	The immediate antimicrobial efficacy at 30 seconds and 10 minutes post-application will be demonstrated if the non-inferiority of the ATE of the investigational products (A, B and C) compared to Positive Control (D) is met (the upper two-sided 95% confidence bound of the post-application microbial counts corrected for Baseline of the investigational products A, B or C compared to the Positive Control should be less than 0.5 log ₁₀).		
Study Methodology:	ASTM Standard Test Method E1173-15		
Study Population:	Healthy subjects at least 18 years of age and of any race. Treatment Day Baseline microbial count requirements are in the range of 5.00 to 7.50 log ₁₀ CFU/cm ² , inclusive, on the groin.		
	Efficacy objectives		
	The objective of this study is to demonstrate immediate (30 seconds and 10 minutes) antimicrobial efficacy of three investigational products (26 ml Project X, 10.5 ml Project X and 5.1 ml Project X) compared to Prevantics® Maxi Swabstick 5.1 ml (active control) on the groin.		
Objectives:	To demonstrate the immediate antimicrobial efficacy at 30 seconds and 10 minutes post-application the following criteria should be met on the groin: - non-inferiority of the ATE of the product A, B and C compared to product D (the upper two-sided 95% confidence bound of the post-application microbial		
	counts corrected for Baseline of the A-D or B-D or C-D should be less than $0.5 \log_{10}$).		
	Exploratory Objectives		
	Evaluation of the investigational products consumption weight (product weight before application – product weight after application).		

	Safety objectives Safety will also be evaluated based on the incidence of adverse events reported during the study and assessment of skin irritation ratings.						
Study Endpoints:	 Log₁₀ CFU/cm² of skin flora at the groin sites before and after each treatment at 30 seconds and 10 minutes. Skin irritation scores (Erythema, Edema, Rash, and Dryness) at each time interval and the incidence of AEs reported during the study. 						
	Treatment	Description	Body Area	Application Time	Drying Time	Treatment Area	
	A – 26 ml Project X	3.15 % w/v CHG / 70% v/v IPA	Groin	120 seconds	min. 180 seconds	1.5" x 5.0" (3.81 cm x 12.7 cm)	
Study Products:	B – 10.5 ml Project X	3.15 % w/v CHG / 70% v/v IPA	Groin	120 seconds	min. 180 seconds	1.5" x 5.0" (3.81 cm x 12.7 cm)	
	C – 5.1 ml Project X	3.15 % w/v CHG / 70% v/v IPA	Groin	120 seconds	min. 180 seconds	1.5" x 5.0" (3.81 cm x 12.7 cm)	
	D – 5.1ml Prevantics® Maxi Swabstick	3.15 % w/v CHG / 70% v/v IPA	Groin	120 seconds	~ 90 seconds	1.5" x 5.0" (3.81 cm x 12.7 cm)	
	Subjects with treatm log ₁₀ /cm ² , inclusive, o					5.00 to 7.50	
	An alpha level of 5% will be used for all analyses.						
	The following descriptive statistics for log ₁₀ CFU/cm ² and for log ₁₀ CFU/cm ² reductions from Baseline will be computed for each treatment, grouped by post application sampling time point (30 seconds, 10 minutes and/or Baseline, by case): mean, median, standard deviation, minimum, maximum, and count.						
	Efficacy Analysis						
Statistical Methods:	A linear regression model for each post-treatment sampling time point of immediate efficacy (30 seconds and 10 minutes post-application) will be used. In the model, the dependent variable used will be the post-treatment bacterial count (\log_{10} CFU/cm ²) and predictors will be the treatment as a fixed effect and the Baseline as a covariate. The ATE corrected for Baseline will be estimated from the model and compared to non-inferiority criteria.						
	Safety Analysis						
	All treated subjects will be considered evaluable for safety. Skin irritation scores will be reported for any subject who is scored with a 1 or more at any observation (treatment day, post-application/prior to 30 seconds and 10 minutes), in any category for any site.						
	Adverse events (including post treatment skin irritation scores of 3), will also be summarized. Summary tables will present incidence rates of adverse events by treatment group for all subjects who enter the treatment period. Listings of adverse events will be provided.						

Contents

obreviat			
2.1		•	
2.2	•		
2.3	Safe	ty objectives	8
3 1			
		,	
_			
		-	
		,	
		•	
		, ,,	
_		•	
		•	
3.8.2			
3.9			
3.10			
3.11	Prote	ocol Modifications	12
3.11	.1	Protocol Amendments	12
3.11	.2	Protocol Deviations	12
		·	
	-		
	-		
4.3	-		
5.1		,	
		•	
	2.1 2.2 2.3 3.1 3.2 3.3 3.4 3.5 3.5.2 3.6 3.6.2 3.7 3.8 3.8.2 3.9 3.10 3.11 3.11 4.1 4.2 4.3 5.1	2.1 Efficients 2.1 Efficients Students Students Students Introduced Students S	obreviations Introduction Study Objectives

	5.1.2	2 Treatment Day	14
	5.2	Microbiological Methods	16
	5.2.	1 Microbial Sample Collection / Cup Scrub Technique	16
	5.2.2	2 Bacterial Enumeration Methods	16
6	6.1	Assessment of Efficacy Efficacy Parameters	
	6.2	Assessment Methods	17
7	7.1	Risk / Benefit Assessment	
	7.2	Potential Benefits	17
8	8.1	Assessment of Safety	
	8.2	Assessment Methods for Skin Irritation	18
	8.3	Adverse Events	18
9	9.1	Statistics Data sets analyzed	
	9.2	Sample Size	20
	9.3	Efficacy Analyses	20
	9.3.	1 Efficacy Analysis	20
	9.4	Safety Analysis	20
	9.5	Procedures for Accounting for Missing, Unused, and Spurious Data	20

2.1 Efficacy objectives

The objective of this study is to demonstrate immediate (30 seconds and 10 minutes) antimicrobial efficacy of three investigational products (26 ml Project X, 10.5 ml Project X and 5.1 ml Project X) compared to Prevantics® Maxi Swabstick 5.1 ml (active control) on the groin.

To demonstrate the immediate antimicrobial efficacy at 30 seconds and 10 minutes post-application the following criteria should be met on the groin:

- non-inferiority of the ATE of the product A, B and C compared to product D (the upper two-sided 95% confidence bound of the post-application microbial counts corrected for Baseline of the A-D or B-D or C-D should be less than 0.5 log₁₀).

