3.1 Overall Study Design and Plan

This study is designed to determine the antimicrobial effectiveness of three treatments (A, B and C), intended for use as Patient Preoperative Skin Preparation. The testing methods are based on the standardized test method ASTM E1173-15, Evaluation of Preoperative, Precatheterization, or Preinjection Skin Preparations, and using the requirements specified by in the 2017 FDA 21 CFR Part 310, Safety and Effectiveness of Health Care Antiseptics; Topical Antimicrobial Drug Products for Over-the-Counter Human Use, Final Rule (December 20, 2017). The immediate antimicrobial efficacy will be evaluated in this study.

At least 100 subjects will be treated bilaterally with two of the four test materials (A, B, C and Positive Control), one per each side of the groin test site. Subjects will undergo at least a 14-day washout period before Treatment Day. During Treatment Day subjects who meet the Inclusion Criteria will be treated with the study products and samples will be taken before and after treatment application. The cup scrub technique will be used for sampling baseline, 30-seconds and 10-minutes on the Treatment Day.

The immediate antimicrobial efficacy at 30 seconds and 10 minutes post-application will be demonstrated if the non-inferiority of the ATE of the investigational products (A, B and C) compared to Positive Control (D) is met (the upper two-sided 95% confidence bound of the post-application microbial counts corrected for Baseline of the investigational products A, B or C compared to the Positive Control should be less than 0.5 log₁₀).

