9.3.1 Efficacy Analysis

A linear regression model for each post treatment sampling time point of immediate efficacy (30 seconds and 10 minutes post-application) will be used. In the model, the dependent variable used will be the post treatment bacterial count (\log_{10} CFU/cm²) and predictors will be the treatment as a fixed effect and the Baseline as a covariate. The ATE corrected for Baseline will be estimated from the model and compared to non-inferiority criteria.

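### Does mixing 'and' with 'or' in the non-inferiority criterion leave it unclear whether products A, B and C are judged one by one or together?

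*Combined protocol and SAP*

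**What the plan says.** The criterion appears four times, always with both conjunctions.

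- Section 2.1 sets a single objective, to "demonstrate immediate (30 seconds and 10 minutes) antimicrobial efficacy of three investigational products". It then requires "non-inferiority of the ATE of the product A, B and C compared to product D", with the upper limit "corrected for Baseline of the A-D or B-D or C-D should be less than 0.5" log10.
- The Objectives row of the synopsis repeats this: "counts corrected for Baseline of the A-D or B-D or C-D should be less than" the same limit.
- The synopsis design text and Section 3.1 say that efficacy "will be demonstrated if the non-inferiority of the ATE of the investigational products (A, B and C) compared to Positive Control (D) is met". Section 3.1 then explains the criterion as "Baseline of the investigational products A, B or C compared to the Positive Control should be less than 0.5" log10.

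Section 9.3.1 fits one linear model per time point, with treatment and baseline as predictors, and adds only this: "The ATE corrected for Baseline will be estimated from the model and compared to non-inferiority criteria". Section 9.3 sets alpha at 5% throughout. Section 9.2 plans at least 50 evaluable sites per product and states that no power calculation was done. Nothing says how the three product results combine into a conclusion.

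**The concern.** Taken word by word, the sentence supports two opposite rules: all three products must pass, or any one is enough. The probable third rule, each product on its own, is never written out. The phrase "The immediate antimicrobial efficacy at 30 seconds and 10 minutes post-application will be demonstrated if the non-inferiority of the ATE" sounds like one study-level conclusion, and Section 9.3.1 merely points back to the criterion.

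If one or two products passed, a report might call the objective met, unmet, or met in part, and cite the protocol each time. Such a choice should not be left until the data are seen. The reading also fixes which error rate is being controlled, and under an any-product rule that rate could exceed one-sided 2.5%.

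**Working it through.** **1. The wording.** In all four places the *and* stands in the list of products under test, and the *or* stands where the limit is attached to contrasts with D. Section 2.1 writes these as three separate differences. A limit stated for one difference *or* another *or* a third is ordinary usage for parallel comparisons: whichever contrast is taken, its upper limit must be below 0.5. Other parts of the plan fit this. Sites are counted per product (9.2), descriptive statistics are given for each treatment (9.3), and the 9.3.1 model yields one difference from D per product. The two time points are joined by *and* throughout, so a product needs both.

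**2. What the reading changes in the analysis.** Three contrasts at two time points give 3 × 2 = 6 upper limits, each compared with 0.5. The model, data, alpha and limit are the same under every reading. Only the summary label differs, and only when one or two products pass.

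**3. Inputs for the error rates.**
- Sites per product: 100 subjects × 2 sides / 4 products = 50, which reproduces the plan's minimum if every site qualifies.
- The upper limit of a two-sided 95% interval is a one-sided 2.5% test.
- Standard error of a contrast: SD × √(2/50) = 0.2 × SD.
- The contrasts share arm D, so their correlation is 0.5 with equal arms and no within-subject correlation.

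**4. Error by reading.**
- Each product alone: at most 2.5% for that product.
- All three required: at most 2.5% for the joint claim.
- At least one false pass, products exactly at the margin at one time point and comfortably inside it at the other: 1 − ∫φ(u)Φ(√2 × 1.96 + u)^m du = 2.5%, 4.5% and 6.3% for m = 1, 2 and 3. With independent contrasts and m = 3 it would be 1 − 0.975³ = 7.3%.

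The 6.3% comes from running three tests at these thresholds. Separate per-product testing runs the same three tests, so its familywise rate is also 6.3%.

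If the two sides of a subject are correlated at 0.5 and all product pairs are used equally (an assumption), the variance factor is 1 − 0.5/3 = 0.833. The chance of at least one false pass is then 4.1%. The per-comparison error falls too: 1.96/√0.833 = 2.147, a tail of 1.6%. So 4.1% should be set against 1.6%, not 2.5%.

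With all three products at the margin at both time points, the chance of at least one false pass is 0.7–1.3% at time-point correlation 0.5 and 1.3–2.3% at 0.7 (within-subject correlation 0 to 0.5).

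**5. How often a split could occur.** The plan gives no SD or true difference, so both are assumed. Settings: 50 sites per product, both time points required, time-point correlation 0.5, within-subject correlation 0, products truly equal to D, 400,000 simulated trials per row.

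| Assumed SD | One given product passes | All three pass | At least one passes | Split |
|---|---|---|---|---|
| 0.5 | 99.8% | 99.3% | 100% | 0.7% |
| 0.6 | 97.4% | 93.4% | 99.9% | 6.5% |
| 0.8 | 79.5% | 59.6% | 95.2% | 35.5% |
| 1.0 | 55.8% | 29.8% | 80.8% | 51.0% |
| 1.4 | 26.4% | 7.6% | 48.8% | 41.2% |
| 2.0 | 11.0% | 1.7% | 24.1% | 22.4% |

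The split is *at least one* minus *all three*; at SD 1.0, 80.8 − 29.8 = 51.0. If each product were truly 0.2 log10 better than D, the split would be under 0.1% at SD 0.6, 4% at 0.8, 22% at 1.0 and 51% at 1.4. These figures show that a split is possible. They do not show that it is likely in this trial.

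**The case for a change.** The strongest case for a change is that a study's sole efficacy criterion should not need interpreting. The four statements repeat the mixed conjunctions instead of resolving them, the conclusion is phrased for the study as a whole, and the statistics section adds nothing. The readings also give different chances of success. At an assumed SD of 1.0 with products equal to D, a joint claim succeeds 29.8% of the time, against 55.8% for one given product.

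Part of this stands. The per-product rule is not put into words, and after a split a reader could argue over whether the single objective was met.

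The rest has less force. The any-product reading, the only one said to raise the error rate, is the least natural, and its 6.3% is shared by separate testing. The realistic choice is between product by product and all three together, and no individual or joint claim exceeds one-sided 2.5% under either. A failed joint claim would not invalidate the interval for a product that passed. A report showing six upper limits against 0.5 lets any reader apply either rule. Section 9.2 disclaims powered evidence of efficacy, and no hierarchy or further decision in the plan hangs on one study-level verdict.

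**Conclusion.** The observation about the text is correct, but no change to the plan is needed. It is a missing detail that analysts will fill sensibly: each product is compared with D on its own, and is non-inferior if its upper limit is below 0.5 log10 at both time points. Writing that out would alter no test, threshold, estimate, alpha or sample size.

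The reading of the text rests on no numerical assumption. The 2.5% ceilings follow from the two-sided 95% interval, taking each interval to have its nominal coverage. The 6.3% further assumes equal arms, no within-subject correlation and all three products exactly at the margin at one time point; it is a familywise rate that applies equally to separate testing. The split probabilities, from under 0.1% to 51%, depend on an assumed SD, true difference and correlations, so they cannot show that the wording will matter here.

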2.2 Exploratory Objectives

Evaluation of the investigational products consumption weight (product weight before application – product weight after application).

2.3 Safety objectives

Safety will also be evaluated based on the incidence of adverse events reported during the study and assessment of skin irritation ratings from Appendix 17.6.

3 Study Design

3.1 Overall Study Design and Plan

This study is designed to determine the antimicrobial effectiveness of three treatments (A, B and C), intended for use as Patient Preoperative Skin Preparation. The testing methods are based on the standardized test method ASTM E1173-15, Evaluation of Preoperative, Precatheterization, or Preinjection Skin Preparations, and using the requirements specified by in the 2017 FDA 21 CFR Part 310, Safety and Effectiveness of Health Care Antiseptics; Topical Antimicrobial Drug Products for Over-the-Counter Human Use, Final Rule (December 20, 2017). The immediate antimicrobial efficacy will be evaluated in this study.

At least 100 subjects will be treated bilaterally with two of the four test materials (A, B, C and Positive Control), one per each side of the groin test site. Subjects will undergo at least a 14-day washout period before Treatment Day. During Treatment Day subjects who meet the Inclusion Criteria will be treated with the study products and samples will be taken before and after treatment application. The cup scrub technique will be used for sampling baseline, 30-seconds and 10-minutes on the Treatment Day.

The immediate antimicrobial efficacy at 30 seconds and 10 minutes post-application will be demonstrated if the non-inferiority of the ATE of the investigational products (A, B and C) compared to Positive Control (D) is met (the upper two-sided 95% confidence bound of the post-application microbial counts corrected for Baseline of the investigational products A, B or C compared to the Positive Control should be less than 0.5 log₁₀).

3.2 Study Type

This is a randomized, single-center, single blind study in healthy subjects. The staff member(s) performing bacterial enumeration will be blinded from the identification of treatment assignment.

3.3 Endpoints

- Log₁₀ CFU/cm² of skin flora at the groin site before and after each treatment at 30 seconds,
 10 minutes.
- Skin irritation scores (Erythema, Edema, Rash, and Dryness) at each time interval and the incidence of AEs reported during the study.

3.4 Randomization and Blinding

The randomization scheme for the study will be provided by the Research facility.

Each subject will receive two treatments. Assignment of products to the left or right side for each body area will be per a computer-generated randomization schedule.

Specific sites of sampling for baseline and post application sampling time points will be randomized.

Randomization will continue until required number of subjects with required treatment day baseline counts is enrolled.

The PI is responsible for ensuring that the randomization is followed. The randomization schedule for the groin sites will be provided in a separate document. The study products will be labeled with the appropriate codes provided in Table 1.

Each subject will be identified by their initials and a subject number for which they qualify. Inclusion subject numbers will be assigned at Treatment day.

- Washout subjects will be assigned numbers starting with 001 and the letter "P": P001
- Treatment subjects will be assigned numbers with 001 and the letter "I": I001

The study products will not be blinded from the PI or other study staff performing the study material application or bacterial sample collections. The staff member(s) performing bacterial enumeration and the statistician will be blinded from the identification of treatment assignment. The study staff performing the bacterial enumeration will not be involved in the study products application or the collection of samples. The Raw Data Sheet sections of the CRF will be maintained separately (from the pages within the CRF which include study treatment identifications) during the conduct phase of the study. The study staff performing the bacterial enumeration will record counts directly onto the Raw Data Sheet pages of the CRF without accessing the subject study documentation folder containing the other CRF pages. The Raw Data Sheets will be compiled with the entire CRF after all data recording have been completed.

The generated randomization scheme will contain the following treatment codes: P1, P2, P3 and P4 to ensure the blinding for the study statistician. The assignment between the treatment codes (P1, P2, P3 and P4) from the randomization scheme and the label treatment codes (A, B, C and D) will be made by the Sponsor in a separate document.

In this study four products will be tested and each subject will receive two products in the same time, one on the left side and the other on the right side. More than 100 randomization schemes will be generated to compensate for the baseline requirement failure and to provide enogh evaluable sites. The block randomization method will be used to ensure equal sample size groups over time. Products will be randomized in blocks of 12 and sampling time points will be randomized in blocks of 6. Randomization scheme will be generated using an electronic online randomizer provided by Urbaniak et al. (2013).

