5.1.2.1.1 Preparation of Groin Test Area

The test site within the groin region (groin test area) is defined as the inner aspect of the uppermost thigh, one inch parallel distance to the inguinal crease and where skin to skin contact is expected. Where subjects present with deep inguinal folds at the crease, the sampling distance from the crease may be increased to avoid skin folds in the sampling area. The corners of each groin test area will be marked directly on the skin using a non-toxic skin marker. Three sampling sites will be numbered within each groin test area, on each side of the groin region. The positioning and numbering of the groin sampling sites are standard for all subjects. Sampling sites on the contra-lateral side of the groin will be numbered in a mirror-image orientation. The three sampling sites within each test area represent one baseline (pre-prep) site and two post-prep sample sites (30 seconds and 10 minutes).

Test sites for the investigational product and active control applicator on the groin will be $1.5'' \times 5''$ (3.81 cm x 12.7 cm) in area, occur at the uppermost inner aspects of both thighs, and appear to be similar in condition.

After groin test areas are marked and sample sites numbered, baseline samples will be collected from the appropriate site per the randomization schedule in each test area using the scrub cup technique (section 5.2.1).

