5.1.2.2 Study Products Application

The randomization schedule will designate the treatment to each side of the groin.

Following baseline sample collection, randomly assigned contra-lateral test areas will be treated with the applicable study products. The post-application sampling times will be randomized among the sampling sites within a test area.

The study products will be applied and the sampling configurations will be performed per the randomization scheme and the Treatment Application Instructions (Appendix 17.6). The duration of each application procedure will be recorded on the appropriate CRF. The study products, body area, application and dry times and treatment area are summarized in Table 2.

Products	Body Area	Application Time	Drying Time	Treatment Area
26 ml Project X (A)	Groin	120 seconds	min. 180 seconds	1.5" x 5.0" (3.81 cm x 12.7 cm)
10.5 ml Project X (B)	Groin	120 seconds	min. 180 seconds	1.5" x 5.0" (3.81 cm x 12.7 cm)
5.1 ml Project X (C)	Groin	120 seconds	min. 180 seconds	1.5" x 5.0" (3.81 cm x 12.7 cm)
Prevantics® Maxi Swabstick 5.1 ml (D)	Groin	120 seconds	90 seconds	1.5" x 5.0" (3.81 cm x 12.7 cm)

Table 2: Study products, body area, application and dry times and treatment area

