5.2 Microbiological Methods

5.2.1 Microbial Sample Collection / Cup Scrub Technique

Quantitative cultures (treatment day baselines and post treatment samples) will be obtained by a modification of the cylinder sampling technique of Williamson-Kligman cup scrub technique following ASTM E1874-14 "Standard Test Method for Recovery of Microorganisms from Skin using the Cup Scrub Technique". To collect the samples, a sterile scrub cup (2.20 cm I.D.) will be placed on the site and held firmly to the skin. 3.0 ml of SSF++ will be pipetted into the cup and the skin will be scrubbed in a circular motion with moderate pressure for 1 minute using a sterile rubber policeman. Using a sterile transfer pipette, the SSF++ will be removed and placed in a sterile test tube. An additional 3.0 ml of fresh SSF++ will be pipetted into the cup and the scrub procedure will be repeated. This solution will be pooled with the first solution collected.

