17.2 Groin Diagram

17.3 Randomization Scheme Example

The randomization will be provided in a separate document.

Randomization number	Body Area	Product Left Side	Product Right Side	Site 1	Site 2	Site 3

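### Nothing in the plan conceals product assignment from the sampler until both baseline samples are taken, although baseline is the covariate and the site entry rule: a cheap improvement

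*Combined protocol and SAP*

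**What the plan says.** The relevant statements are spread over several sections of the protocol.

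- **Who is unblinded.** Section 3.4: "The study products will not be blinded from the PI or other study staff performing the study material application or bacterial sample collections". Enumerators and the statistician are blinded.
- **What counts as a sample collection.** Section 5.2.1: "Quantitative cultures (treatment day baselines and post treatment samples) will be obtained" by the cup scrub. Baselines are therefore included.
- **How the baseline site is chosen.** Section 5.1.2.1.1: "baseline samples will be collected from the appropriate site per the randomization schedule in each test area".
- **What else the schedule holds.** Section 5.1.2.2: "The randomization schedule will designate the treatment to each side of the groin". The example in 17.3 has a column headed "Product Left Side", one for the right side, and Sites 1 to 3, all in one row.
- **Order of events.** Section 5.1.2.2: "Following baseline sample collection, randomly assigned contra-lateral test areas will be treated with the applicable study products".
- **Who supplies the schedule.** Section 3.4: "The randomization scheme for the study will be provided by the Research facility". It uses codes P1-P4, which the sponsor links to A-D in a separate document.

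Baseline has two roles in the analysis. It is the covariate in the regression at each time point (9.3.1). It also decides, for each side separately, whether a site enters the modified intent-to-treat set, through the range 5.00 to 7.50 log10 CFU/cm² (9.1).

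**The concern.** Baseline is taken before any product touches the skin, so it could be collected without knowledge of assignment. The plan does not arrange this. It has unblinded staff work from a schedule that, in its example layout, carries the side assignment beside the site order.

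Blinded counting protects the reading of the plate but not what reaches the plate. Recovery depends on two one-minute manual scrubs at a pressure that the operator judges (5.2.1). Baseline and post-treatment samples come from different sites within the test area (5.1.2.1.1), so a firmer baseline scrub could raise the recorded baseline without stripping the site sampled later.

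The direction matters in a non-inferiority comparison. A baseline recorded too high on Project X sides lowers the adjusted A-D, B-D or C-D difference and makes it easier to meet the 0.5 log10 criterion. The same distortion could move sites into or out of the modified intent-to-treat set. It would also pass in full into the descriptive log reductions (9.3).

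**Working it through.** **The plan's own figure.** 100 subjects × 2 sites ÷ 4 products = 50 sites per product. This matches the minimum in 9.2, provided that no site fails the baseline range; 3.4 provides extra randomization schemes to cover failures. Section 9.2 says that no sample size calculation was done, so there is no SD or power to reproduce.

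**Inputs from the plan.** 50 sites per product (9.2); margin 0.5 log10 and upper bound of a two-sided 95% interval, that is 2.5% one-sided (3.1); baseline as covariate (9.3.1); range 5.00 to 7.50 (9.1).

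**Inputs assumed, because the plan gives none.** Baseline distortion δ between a test product and D; baseline slope β; residual SD; independence of all sites, although two sites come from each subject.

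**Effect on the adjusted difference.** A distortion δ that comes only from sampling technique moves the adjusted difference by −β × δ. With β = 0.4 and δ = 0.2, the shift is −0.08 log10. A simulation with β = 0.5 and δ = 0.2 gave a mean shift of −0.096, against −0.10 from the formula.

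**Effect on type I error at the margin.**
- SE = 1.0 × √(2/50) = 0.20.
- Without distortion the error is 2.5%.
- With distortion it is Φ(0.08/0.20 − 1.97) = Φ(−1.57) = 5.8%. With 1.96 in place of the t value it is 5.9%.

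**Range over assumed values** (δ 0.1 to 0.3, β 0.3 to 0.6, SD 0.8 to 1.2):
- Lowest: shift 0.1 × 0.3 = 0.03, SE 1.2 × 0.2 = 0.24, Φ(0.125 − 1.97) = 3.2%.
- Highest: shift 0.3 × 0.6 = 0.18, SE 0.8 × 0.2 = 0.16, Φ(1.125 − 1.97) = 20%.
- With δ = 0 the error stays at 2.5%, and the documents do not exclude that value.

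**Distortion needed to use up the whole margin.** 0.5/β, which is 0.5 log10 at β = 1.0 and 2.5 log10 at β = 0.2.

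**Effect on eligibility** (assumed baseline SD 0.5, upward shift 0.1). The qualifying share goes from 84.1% to 88.5% if the true mean is 5.5, and from 97.6% to 98.4% if it is 6.0. At a mean of 6.5 it falls from 97.6% to 96.3%, because the upper limit then binds.

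**Comparison with the post-treatment samples.** A 0.2 log10 distortion there enters the difference without being multiplied by the slope: Φ(0.2/0.20 − 1.97) = 17%, against 5.8% for the same distortion at baseline.

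**The case against.** The strongest reply has five parts.

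1. **Knowledge at baseline is not stated.** The schedule carries P1-P4, and the link to A-D is a separate sponsor document. The table in 17.3 is a blank example, and the working schedule is not part of the documents. A reader might infer that the sampler sees Project X or control before scrubbing; no section says this. That stands. The codes are, however, explained only as blinding the statistician. Products are labelled with the Table 1 codes, so whoever applies them needs the link. Once it is known, every later row can be read. The plan does not say when staff receive it.
2. **The count has protection.** A reader might infer that baseline is wholly open to influence. It is not. Enumerators neither sample nor apply product, and they record on sheets kept apart (3.4). Cup, fluid volume and scrub time are fixed (5.2.1), and entry is a numeric range. Plates are incubated for about 72 hours (5.2.2), so staff cannot use the baseline count to choose whom to treat. This limits the exposure to technique and handling but does not remove it.
3. **The distortion is invented.** This is correct. Its size, the slope and the SD are all assumed, and the arithmetic shows only what would follow.
4. **The outcome samples are the larger route.** This is also correct, and the change proposed here leaves that route open. Concealing baseline is still worthwhile because it can be done with the same staff before any device is in use.
5. **Single-blind sampling is declared.** Sections 3.2 and 3.4 disclose it, so it is a design choice and not an error. Disclosure does not explain why assignment should be available before baseline.

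**Conclusion.** The point holds as a cheap improvement. The plan leaves baseline samplers unblinded, ties their site selection to the schedule that assigns product, and describes no step that conceals assignment until both baselines are taken.

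The documents do not support a finding that samplers know the product at baseline, or that any bias has occurred. Its size is unknown. The shift of 0.08 log10 and the rise from 2.5% to about 5.8% are an illustration that rests on a 0.2 log10 distortion, slope 0.4, residual SD 1.0 and 50 independent sites per product. None of the first three comes from the plan.

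Concealment would protect the covariate and the site-level entry rule. It would not protect the 30-second and 10-minute samples.

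**What to change.** Amend 3.4, 5.1.2.1.1 and 17.3 as follows.

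- For baseline, the sampler receives a sheet with only the subject number and the order of Sites 1 to 3.
- The left and right product assignment is kept in a sequentially numbered sealed envelope. It is opened only after both baseline samples are in their tubes, and the opening time is entered on the CRF.
- Because the research facility supplies the schedule, the text should name the role that prepares and holds the envelopes.
- State as a limitation that the post-treatment samples are still collected by unblinded staff.

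Splitting the schedule is feasible because products and sampling time points are already randomized separately, in blocks of 12 and of 6 (3.4). If the site already works this way, a statement of the procedure in 3.4 is enough.

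The cost is one extra sealed sheet per subject and one CRF field. The same staff carry out all steps, and the number of sites, the margin and the analysis do not change.
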